5 STUDY ENROLLMENT AND WITHDRAWAL

Subjects who are diagnosed with CAP in EDs, urgent care facilities, and clinics will be screened for eligibility. Screening will continue until 400 subjects are enrolled cumulatively across all the study sites. The study will recruit potential subjects from children who are diagnosed with CAP and who are initiated on antibiotic therapy using oral beta-lactam therapy (amoxicillin, amoxicillin-clavulanate, cefdinir) by healthcare providers in EDs, outpatient clinics, and urgent care centers at the study sites. Potential subjects will be identified at any time following clinical diagnosis of pneumonia. Other forms and/or mechanisms of recruitment may also be used. The local IRB will approve recruitment materials prior to use.

Subject Inclusion and Exclusion Criteria must be confirmed by a study clinician licensed to make medical diagnoses.

No exemptions are granted on Subject Inclusion/Exclusion Criteria in DMID-sponsored studies. Questions about eligibility will be directed toward the DMID Medical Officer.

5.1 Subject Inclusion Criteria

Eligible subjects may be included in the study if they meet ALL of the following criteria at the Enrollment Visit (Day -3 to -1):

1. Age 6 – 71 months
2. Provider diagnosis of CAP and prescription of antibiotic therapy with amoxicillin¹, amoxicillin-clavulanate¹, or cefdinir²
¹ amoxicillin or amoxicillin-clavulanate prescribed at a minimum amoxicillin dose of 60 mg/kg/day
² cefdinir prescribed at a minimum dose of 10 mg/kg/day
3. Parental report of clinical improvement³
³ based on lack of either subjective or known fever (temperature $\geq 38.3^{\circ}\text{C}$ in the preceding 24 hours); current respiratory rate no greater than 50 breaths/minute (<2 years of age) or 40 breaths/minute (≥ 2 years of age); and current grade of cough <3.
4. Ability of a parent or guardian to understand and comply with the study procedures and be available for all study visits
5. Signed written informed consent by a parent or guardian

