3.2 Study Outcome Measures

3.2.1 Primary Outcome Measures

The primary endpoint/outcome measure is the DOOR at Outcome Assessment Visit #1.

DOOR is defined as follows:

- I. Each subject is evaluated according to the ordinal composite outcome (See Table 1 below) and assigned an outcome rank ranging from 1-8.
- II. Desirability of Outcome Ranking (DOOR) is then assigned according to two rules:
 - (i) When comparing two subjects with different ordinal responses, the subject with a better ordinal response receives a higher rank.
 - (ii) When comparing two subjects with identical ordinal responses, the subject with fewer days of antibiotic use receives a higher rank.

The ordinal composite outcome involves an assessment of whether the subject has an adequate clinical response and whether they have experienced any solicited events as defined below.

Table 1. Ordinal Outcome

	Adequate clinical response¹ (Assessed at Outcome Assessment Visits #1 and #2)	Solicited events³ (Assessed at Outcome Assessment Visits #1 and #2)
1	Yes, with resolution of symptoms ²	None
2	Yes, with resolution of symptoms ²	Mild (Grade 1)
3	Yes, with resolution of symptoms ²	Moderate (Grade 2)
4	Yes, with resolution of symptoms ²	Severe (Grade 3)
5	Yes, with persistent symptoms of fever, tachypnea, or cough	None or any grade
6	No, with ED/clinic visit but no hospitalization	None or any grade
7	No, with hospitalization	None or any grade
8	Death from any cause	

¹Adequate clinical response is defined as the absence of a medically attended visit to an ED or outpatient clinic or hospitalization for persistent or worsening pneumonia that occurs after randomization and receipt of at least one dose of study drug.

- Persistent or worsening pneumonia is defined as receipt of a non-study systemic antibiotic for pneumonia or treatment for a complication of pneumonia, including drainage of pleural fluid, placement of a chest tube, video assisted thoracoscopic surgery, or thoracotomy procedures.
- Note: Receipt of a non-study antibiotic will not be regarded as satisfying this definition if it is related to a new diagnosis that is unrelated to the prior diagnosis of pneumonia.

²Resolution of symptoms is defined as the absence of all of the following:

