- Oral, rectal, axillary, or tympanic temperature $\geq 38.3^{\circ}\text{C}$ (100.9°F), confirmed by repeat measurement after at least 15 minutes, in the 24 hours preceding the Outcome Assessment Visit or measured at the Outcome Assessment Visit, unless attributed to a new process that is unrelated to the prior diagnosis of pneumonia;
- Elevated respiratory rate (RR >50 breaths/minute for children <24 months of age and >40 breaths/minute for children 24-71 months of age) at the time of the Outcome Assessment Visit;
- Presence of cough grade 2 or 3 at the Outcome Assessment Visit, (defined in Table 2).

³Solicited events (Table 3) will be captured daily until Outcome Assessment Visit #2; thereafter, parents/legal guardians will report symptoms based on memory aid and medical interview by

study staff. For those with multiple solicited events, the ordinal response table will be based upon the most severe solicited event.

Table 2: Severity of Cough

Symptom	Mild (Grade 1)	Moderate (Grade 2)	Severe (Grade 3)
Cough	Occasional coughing (less than 4 times hourly)	Frequent coughing (4 or more times an hour), interferes with sleep)	Almost constant coughing (never free of cough), makes sleep nearly impossible

Table 3. Solicited Events Grading

Symptom	Mild (Grade 1)	Moderate (Grade 2)	Severe (Grade 3)
Irritability	More irritable or fussy than usual but can be consoled; no interference with smiling/playing	Irritability or fussiness that is difficult to console and interferes with smiling and playing	Irritability or fussiness that lasts for more than 4 consecutive hours in a 24 hour period or cannot be consoled
Vomiting	1 episode/day	2-3 episodes/day	≥4 episodes/day
Diarrhea	Looser than normal stools occurring 3-6 times/day	Looser than normal stools occurring >6 times/day	Bloody diarrhea, or diarrhea that requires medical intervention, laboratory testing, or hospitalization
Allergic Reaction	Localized rash or pruritus without rash	Diffuse rash (maculopapular or urticarial)	Generalized rash consistent with Stevens-Johnson Syndrome, erythema multiforme, or toxic epidermal necrolysis; anaphylaxis; or angioedema
Stomatitis	Oral lesions associated with parenteral report of mild oral discomfort	Oral lesions associated with difficulty swallowing, but able to eat and drink	Oral lesions associated with inability to swallow solids or liquids; requires medical intervention, IV fluids, or hospitalization

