7.2 Enrollment/Baseline

At the Enrollment Visit, study staff will obtain written informed consent from the parent(s)/guardian(s) for the primary study and request consent for collection of throat swabs and stool specimens for future use. Declination to participate in collection of future use samples will not affect participation in the primary study. After the parent/guardian has had the opportunity to ask questions and has signed the informed consent document, the following activities will be performed by the study staff:

- Eligibility criteria will be reviewed;
- A complete medical history and sociodemographic data will be obtained by interview with the subject's parent(s)/legal guardian;

-
- A physical assessment will be performed to determine general appearance, hydration status; vital signs, including temperature, heart rate, and respiratory rate; an assessment of work of breathing; and presence of skin rash; additionally, if indicated by the physical assessment or medical history, a physical examination by a study clinician may occur;

** Note: physical assessments may be performed by physicians, advanced practice nurses, physician assistants, or nurses.*

- An initial assessment of clinical response will be obtained to include report of subjective fever, maximum temperature in the past 24 hours (if taken), and an assessment of improved activity and appetite since initiating antibiotic therapy;
- All concomitant medications taken within 30 days of signing the informed consent form will be recorded;
- Subjects who meet eligibility criteria will be enrolled in AdvantageEDCSM and randomly assigned to one of two arms: standard course therapy (5 days of active medication) vs. short course therapy (5 days of matching placebo);
- Study product will be dispensed and study staff will review the study product with the subject's family and review the study product storage and dosing instructions;

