6.4. Covariates and Subgroups

Subjects will be recruited from multiple clinical sites, but randomization will not be stratified by site. Randomization will use a total of 12 strata, with stratification by 1) age group (<24 months vs. 24-71 months), 2) initially prescribed antibiotic (amoxicillin vs. amoxicillin-clavulanate vs. cefdinir), and 3) treatment site (emergency department vs. outpatient clinic/urgent care facility).

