6.5.3. Resolution of Symptoms at OAV#1 or OAV#2

Resolution of symptoms is defined as the absence of all of the following:

- Fever at the OAV, as defined above
- Elevated respiratory rate (RR >50 breaths/minute for children <24 months of age and >40 breaths/minute for children 24-71 months of age) at the time of the Outcome Assessment Visit (VS1.RESPB);
- Presence of cough grade 2 or 3 at the Outcome Assessment Visit (ACRCGHSV)

If the subject died at any point of participation in the study, then the subject will be analyzed as not having resolution of symptoms at either Outcome Assessment Visit. Otherwise, if the subject did not have adequate clinical response at OAV#1 or OAV#2, then the subject will be analyzed as not having resolution of symptoms at the respective Outcome Assessment Visit(s). Otherwise, if fever, elevated respiratory rate, or presence of grade 2 or 3 cough is indicated at OAV#1 or OAV#2, then the subject does not have resolution of symptoms at the respective Outcome Assessment Visit (regardless of whether some components of the resolution of symptoms are missing). Otherwise, if fever, respiratory rate, and presence of cough are all non-missing and are indicated as 'No' at OAV#1 or OAV#2, then the subject has resolution of symptoms at the respective Outcome Assessment Visit. Otherwise, resolution of symptoms is missing at the Outcome Assessment Visit.

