8.2.4. Resolution of Symptoms at Outcomes Assessment Visits #1 and #2

Separately for Outcome Assessment Visit #1 and #2, using CC-V1 and CC-V2, respectively, a forest plot of 95% confidence intervals for the risk difference of lack of resolution of symptoms as well as the following: (1) fever (as defined in Section 6.5.2) (2) Elevated respiratory rate (RR >50 breaths/minute for children <24 months of age and >40 breaths/minute for children 24-71 months of age) at the time of the Outcome Assessment Visit; and (3) Presence of cough Grade 2 or 3 at the Outcome Assessment Visit will be given (Figure 9 and Figure 10). Results will also be reported in tables (Table 24 and Table 25), and tests for differences in proportions between treatment arms will be given by Fisher's exact tests. The Newcombe method with continuity correction will be used to compute all 95% confidence intervals for risk differences.

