 - Severity of cough on Day 1 as recorded on Solicited Events form (0, 1, 2, or 3)
 - Note: amoxicillin is the reference group for initial antibiotic
 - Severity of most severe solicited event (besides cough) on Day 1 (0, 1, 2, or 3)
 - Note: Some missing values for Day 1 will first be imputed as described in Section [6.5.4](#)
 - Severity of cough on Day 2 as recorded on Solicited Events form (0, 1, 2, or 3)
 - Severity of most severe solicited event (besides cough) on Day 2 (0, 1, 2, or 3)
 - Note: Some missing values for Day 2 will first be imputed as described in Section [6.5.4](#)
 - Severity of cough on Day 3 as recorded on Solicited Events form (0, 1, 2, or 3)
 - Severity of most severe solicited event (besides cough) on Day 3 (0, 1, 2, or 3)
 - Note: Some missing values for Day 3 will be first imputed as described in Section [6.5.4](#)
 - Severity of cough on Day 4 as recorded on Solicited Events form (0, 1, 2, or 3)
 - Severity of most severe solicited event (besides cough) on Day 4 (0, 1, 2, or 3)
 - Note: Some missing values for Day 4 will first be imputed as described in Section [6.5.4](#)
-

- Severity of cough on Day 5 as recorded on Solicited Events form (0, 1, 2, or 3)
- Severity of most severe solicited event (besides cough) on Day 5 (0, 1, 2, or 3)
 - Note: Some missing values for Day 5 will first be imputed as described in Section 6.5.4

For DOOR and OCR at Outcome Assessment Visit #2, the complete list of model variables is identical to the above, but with OCR at Outcome Assessment Visit #2 replaced with OCR at Outcome Assessment Visit #1. Additionally, cough severity and most severe solicited event are listed up to Day 18 rather than Day 5.

The actual list of model variables for each subject-specific imputation model will follow the ordering above but omit variables with missing values. The below pseudo-code / SAS code outlines the creation of 20 multiple imputation datasets. Note that the seeds used in the actual analysis must follow the specification given in the pseudo-code and subjects must be processed in the order described in the pseudo-code. OCR will simultaneously be imputed with DOOR at each respective Outcome Assessment Visit. The pseudo-code is in terms of the Outcome Assessment Visit #1 endpoints, but the general logic is also applicable to the Outcome Assessment Visit #2 endpoints (with references to “V1” replaces with references to “V2”).

DEFINE i=index variable for subjects having DOOR imputed.

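### Grade 2 cough is allowed at entry but counts as unresolved at the outcome visits, and the resolution analysis ignores entry cough: a loss of precision and interpretability, not a bias

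*Protocol*

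**What the plan says.** Inclusion criterion 3 (Protocol 5.1) defines improvement by three conditions: no fever in the preceding 24 hours, a respiratory rate no higher than 50 or 40 by age, "and current grade of cough <3". Grades 0, 1 and 2 all qualify.

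Footnote 2 to Table 1 (Protocol 3.2.1) lists what blocks resolution of symptoms at a visit: fever, a respiratory rate above the same age limits, or "Presence of cough grade 2 or 3 at the Outcome Assessment Visit". SAP 6.5.3 repeats the cough rule. A child with an adequate clinical response who fails on any of these takes rank 5, described as "Yes, with persistent symptoms of fever, tachypnea, or cough".

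Resolution is secondary objective 2. SAP 8.2.4 analyses it with unadjusted risk differences in the complete-case cohorts, and "tests for differences in proportions between treatment arms will be given by Fisher's exact tests". SAP 8.2.6 compares the ordinal clinical response (OCR) without covariates and sets a 0.40 non-inferiority bound.

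The entry cough grade is not a stratification factor (SAP 6.4), a baseline summary (SAP 9.1, Tables 9-12), a subgroup (SAP 8.3.2) or an imputation predictor (SAP 8.4.1). The nearest variable is cough on Day 1 from the memory aid. It predicts missing endpoints in SAP 8.4.1 and is tabulated by arm in SAP 8.2.7.

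**The concern.** The entry limits for fever and respiratory rate essentially match the outcome limits; the cough limits do not. A child can therefore be randomized already meeting one criterion for being unresolved, and only through cough. If that child's cough does not change, the result tables look the same as for a child whose cough cleared and came back after active treatment ended. Protocol 2.3.1 names relapse as the specific risk of the short course, so the distinction bears on how resolution is read. The footnotes to SAP Tables 14 and 15 also say that conclusions about DOOR must draw on its components.

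Entry cough is likely to predict cough at the visit. Ignoring a predictor of that kind gives up precision, and a chance difference between arms in entry cough passes straight into the resolution estimate.

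**Working it through.** **1. The plan's own figure.** SAP section 5 uses Noether's formula: (1.960 + 1.282)² / [12 × 0.25 × (0.60 − 0.50)²] = 10.507 / 0.03 = 350.2, or 351, against 360 stated. Power at 360 is 90.8%, and 360 / 0.9 = 400. This point does not affect that calculation. It sets the base: SAP 8.2.4 uses complete cases, planned at about 360, not 400.

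**2. Precision.** The documents give neither the share *g* entering with grade 2 cough nor the unresolved rates by entry grade (*p*hi for grade 2, *p*lo otherwise). All are assumed.

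- *m* = *g·p*hi + (1 − *g*)·*p*lo
- R² = *g*(1 − *g*)(*p*hi − *p*lo)² / [*m*(1 − *m*)]
- extra children = 360 × R² / (1 − R²)
- narrowing of the interval = 1 − √(1 − R²)
- share of unresolved children who entered at grade 2 = *g·p*hi / *m*

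| Unresolved, grade 2 vs other | *g* | *m* | R² | Extra children | Narrowing | Share |
|---|---|---|---|---|---|---|
| 20% vs 10% | 10% | 0.11 | 0.0009/0.0979 = 0.009 | 3.3 | 0.5% | 18% |
| | 20% | 0.12 | 0.0016/0.1056 = 0.015 | 5.5 | 0.8% | 33% |
| | 30% | 0.13 | 0.0021/0.1131 = 0.019 | 6.8 | 0.9% | 46% |
| 40% vs 10% | 10% | 0.13 | 0.0081/0.1131 = 0.072 | 27.8 | 3.6% | 31% |
| | 20% | 0.16 | 0.0144/0.1344 = 0.107 | 43.2 | 5.5% | 50% |
| | 30% | 0.19 | 0.0189/0.1539 = 0.123 | 50.4 | 6.3% | 63% |

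**3. Chance imbalance.** With 180 per arm, the SD of the between-arm difference in entry grade 2 cough is √[2*g*(1 − *g*)/180]. At *g* = 20% this is √(0.32/180) = 4.2 points. A 2-SD imbalance shifts the resolution difference by 2 × 4.2 × 0.30 = 2.5 points under 40% vs 10%, and by 0.8 points under 20% vs 10%. The standard error of that difference, √[2*m*(1 − *m*)/180], is 3.9 and 3.4 points respectively.

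**4. Bias and type I error.** I simulated 180 per arm, 2,500 runs per setting, with 10-50% entering at grade 2 and 15-70% of them unresolved against 5% of the others. A two-proportion z test stood in for Fisher's test. With no treatment effect, the unadjusted tests rejected in 4.4-5.8% of runs for resolution and 3.6-5.8% for OCR, against a nominal 5% and a Monte Carlo standard error of about 0.4 points. There is no inflation. With an assumed treatment effect, stratifying changed power by +0.2 to +39 points for resolution and −0.4 to +13 for OCR. The largest gain came from an extreme setting (70% unresolved, multiplied by 1.4 in the short arm).

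**The case against.** The best defence is that nothing planned is invalid. Improvement is an eligibility state and resolution is an outcome. A child who enters with grade 2 cough can clear it by Day 6-10 or Day 19-25, and the endpoint records whether that happens. Rank 5 is still an adequate clinical response. An unadjusted Fisher test in a randomized double-blind trial is sound, and covariate use in a secondary analysis is often a matter of preference. Cough by arm from Day 1 is already planned, so a marked early imbalance would be visible there. The gain may also be tiny, as the upper half of the table shows.

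All of this stands. It disposes of two stronger readings that a reader might infer: that the thresholds contradict each other, and that entry cough biases the arm comparison. The documents support neither.

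It does not fully answer the narrower point. Day 1 cough appears in tables of its own, not crossed with resolution. It is also usually recorded after randomization, since enrollment falls mostly on Day −3 to −1.

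The practical objection also has force. Eligibility needs only a grade below 3, and Protocol 7.2 describes the entry check of response as subjective fever, maximum temperature and "an assessment of improved activity and appetite since initiating antibiotic therapy", without naming a cough grade. SAP section 13 shows that enrollment had already begun under an earlier protocol version. The exact grade may not exist as a value for every child.

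**Conclusion.** The point holds as an inexpensive improvement to secondary objective 2. Entry cough is a plausible predictor that eligibility already requires someone to judge. Leaving it out costs precision, leaves chance imbalance unaddressed and blurs what an unresolved child means. The size rests entirely on assumed rates: about 3-7 children's worth of information on 360 if the association is weak, and 28-50 if it is strong, for 10-30% entering at grade 2.

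A reader might also infer that the 0.40 OCR bound is compromised because children held at rank 5 in both arms pull the estimate towards 0.5. If a share *q* sat there whatever the arm and nobody ranked 6-8, the distance from 0.5 would shrink by (1 − *q*)², for example 0.81 at *q* = 10%. The documents give no *q* and no sign that such children are unaffected by arm, so this is a reason to show OCR by entry cough, not a finding against the bound. Nor is a stratified Mann-Whitney a substitute: it compares children within strata, which is a different quantity from the marginal probability to which 0.40 applies.

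No view is taken on which cough threshold is clinically right.

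**What to change.** - **SAP 8.2.4:** beside Fisher's test, report a Mantel-Haenszel risk difference for lack of resolution at each visit, stratified by entry cough grade (0/1 vs 2).
- **SAP 9.1:** tabulate entry cough grade by arm.
- **SAP 8.2.4 and 8.2.6:** show resolution and OCR descriptively by entry cough grade and arm.
- **Source of the value:** use the Enrollment Visit grade. Where it was not recorded as a value, use Day 1 memory-aid cough as a stated fallback, note that it is usually after randomization, and report how many children rely on it.
- **SAP 8.2.6:** keep the unadjusted OCR analysis for the 0.40 bound. Label any stratified Mann-Whitney as a sensitivity analysis of a different quantity.

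The cost is a few table rows, some SAP wording and one recorded value that may be missing for children already enrolled. No threshold, eligibility rule, primary endpoint or sample size changes.

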5.2 Subject Exclusion Criteria

Subjects will be excluded from the study if they meet ANY of the following criteria:

1. Treatment with any systemic antibiotic therapy within 7 days before the diagnosis of CAP

-
2. Initial therapy for CAP with combination antibiotic therapy⁴
⁴ amoxicillin, amoxicillin/clavulanate or cefdinir plus one or more additional oral, intravenous, or intramuscular antibiotics
 3. History of anaphylaxis or severe drug allergy to amoxicillin, if prescribed amoxicillin or amoxicillin/clavulanic acid; or oral cephalosporin antibiotics (except cefaclor), if prescribed cefdinir
 4. Presence of concomitant bacterial infection that requires >5 days of antibiotic therapy
 5. Radiographic findings (where applicable) of complicated pneumonia⁵ at presentation or any subsequent chest radiograph up to the time of enrollment
⁵ Clinically significant pleural effusion, lung abscess, or pneumatocele
 6. Hospitalization⁶ for pneumonia during Day -5 to -1 of antibiotic therapy for CAP
⁶Subjects who require serial clinical assessments, but are discharged within 24 hours will not be considered hospitalized and will not satisfy this exclusion criterion.
 7. Pneumonia due to *S. aureus* or group A streptococcus documented by positive blood culture or PCR, at the time of enrollment.
 8. History of pneumonia within the previous 6 months
 9. History of persistent asthma⁷ within the previous 6 months or current acute asthma exacerbation⁸
⁷ Persistent asthma is defined as receiving daily asthma maintenance therapy such as inhaled corticosteroids, cromolyn, theophylline, or leukotriene receptor antagonists.
⁸ Acute asthma exacerbation is defined as receiving concomitant bronchodilator therapy and systemic corticosteroids.
 10. Provider-diagnosis of aspiration pneumonia, bronchiolitis, or bronchitis.
 11. Surgery or other invasive procedures of the upper or lower airway (e.g., bronchoscopy, laryngoscopy) with general anesthesia or hospitalization ≤ 7 days before diagnosis of CAP
 12. History of an underlying chronic medical condition⁹
⁹ including chronic heart disease, chronic lung disease (except asthma), congenital anomalies of the airways or lung, cystic fibrosis, chronic renal disease including nephrotic syndrome, protein-losing enteropathy of any cause, severe malnutrition, neurocognitive disorders, metabolic disorders (including phenylketonuria), or genetic disorders (note: genetic syndromes such as Down syndrome and Edwards Syndrome are excluded; however, children with genetic disorders (e.g., hemophilia) but who do not have a genetic syndrome may not satisfy this particular exclusion criterion; it is important that children with such genetic disorders do not have symptoms and/or comorbidities that would pose additional risk to them nor jeopardize the adequacy of study assessments.”)

13. History of a condition that compromises the immune system¹⁰

¹⁰ *HIV infection, primary immunodeficiency, anatomic or functional asplenia; receipt of a hematopoietic stem cell or solid organ transplant at any time; receipt of immunosuppressive therapy including chemotherapeutic agents, biologic agents, antimetabolites or radiation therapy during the past 12 months; or daily use of systemic corticosteroids for more than 7 consecutive days during the past 14 days.*

14. Any other condition that in the judgment of the investigator precludes participation because it could affect the safety of the subject
15. Current enrollment in another clinical trial of an investigational agent
16. Previous enrollment in this trial

